6.2. PK Results Evaluations

6.2.1 Calculation of Primary Endpoints

- C_{max} will be obtained directly by observing the plot of PK curve;
- AUC_{0-6h} and AUC_{0-24h} will be calculated with trapezoid method;
- $AUC_{0-\infty}$ will be calculated with extrapolation method.

6.2.2 Calculation of Secondary Endpoints

- t_{max} is an observed values, at which C_{max} is achieved.

6.2.3 Missing Data Handling

Missing data includes missing samples and missing data points for various cases, such as:

- (1) Missed scheduled points for sampling;
- (2) Tube breakage;
- (3) Inadequate amount of sample for analysis;
- (4) Unexpected reasons (i.e., medical condition such that the subject is unable to complete the study).

A table of all missing samples will be provided with explanations.

6.2.4 Relative Bioavailability

The relative bioavailability of Treatment-A over Treatment-B (IM) can be defined as follows:

$$RBA = \frac{AUC_{0-\infty}^A}{AUC_{0-\infty}^B}$$

6.3. Safety Assessment

- (1) Changes in vital signs and ECG will be analyzed between Screening, designated post-dose time points and EOS;
- (2) Changes in serum potassium and glucose at study baseline, designated post-dose time points and EOS;
- (3) Physical examinations at Screening, and at the end of the last Dosing Visit, or study termination;
- (4) The results of laboratory tests, including CBC (with differential), metabolic panel and UA, will be assessed and compared between data at Screening and that at EOS;

(5) AEs will be observed and documented as described in [Sections 5.3.7](#) and [7.2.1](#). AEs of each study treatment will be assessed per seriousness, severity, expected/unexpected, etc. The occurrence of AEs as absolute case number and relative ratio will be compared between each treatment.

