- Epinephrine concentrations versus time; and
- The mean and standard deviation of study endpoints will be estimated. The variances within and between subjects will be estimated.

4) Statistical Analysis:

All endpoint will be listed and compared between treatments.

VI. Safety Evaluations

- 1) Monitor changes in vital signs and ECG will be analyzed between Screening, designated post-dose time points and EOS;
- 2) Heart rate, and systolic and diastolic blood pressure will be measured at baseline, 5 ± 2 min, 15 ± 5 min, 60 ± 5 min, 120 ± 15 min and 24 ± 2 hours after dosing;
- 3) Monitor serum potassium and glucose at study baseline, designated post-dose time points and EOS;
- 4) Physical examinations at Screening, and at the end of the last Dosing Visit, or study termination;

- 5) The results of laboratory tests, including CBC (with differential), metabolic panel and UA, will be assessed and compared between data at Screening and that at EOS;
- 6) All subjects will be queried for ADEs. All ADEs must be recorded and assessed.

Table of Contents

1. INTRODUCTION AND RATIONALE.....	14
1.1. Introduction of the Drug Product.....	14
1.2. Mechanism of Action	15
1.3. Indications and Dose	15
1.4. Pharmacokinetics (PK) and Pharmacodynamics (PD) Profile	15
1.5. Contraindications, Warnings, Precautions, and Adverse Reactions.....	17
1.5.1. Contraindications	17
1.5.2. Warnings and Precautions.....	17
1.5.3. Adverse Reactions	18
1.6. Drugs with Strong Impact on PK or PD	18
2. OBJECTIVES	20
2.1. Objective.....	20
2.2. Primary Endpoints	20
2.3. Secondary Endpoint.....	20
3. INVESTIGATORS AND STUDY SITES.....	21
3.1. Principal Investigator(s)	21
3.2. Investigational Site(s).....	21
3.3. Laboratory	21
4. MATERIALS AND METHODS	22
4.1. Study Design.....	22
4.2. Study Subjects	22
4.2.1. Sample Size.....	22
4.2.2. Subject Enrollment.....	22
4.2.3. Inclusion Criteria:	22
4.2.4. Exclusion Criteria	23
4.3. Randomization Procedures	23
4.3.1. Subject Identification Assignment.....	23
4.3.2. Subject Randomization	24
4.4. Dispensing, Returning, and Storage of Material and Drug Supplies.....	24
4.5. Study Drugs Administration and Training	25
4.5.1. Training for Correct Use of MDI Inhaler	25
4.5.2. Preparation and Training of MDIs at the Dosing Visit.....	25
4.5.3. Detailed MDI Dosing Procedure	26

4.5.4. IM Injection Procedure	27
4.6. Blinding Methodology and Procedure.....	27
4.7. Unblinding	27
5. STUDY PROCEDURE.....	29
5.1. Global Plan	29

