5.3.2. Pre-dose Activities

At each Dosing Visit, the following review and verification will be performed prior to study drug administration:

- (1) A urine or serum pregnancy test must be performed on all female subjects. If it is positive, the subject will be terminated from the study;
- (2) Any concomitant medication since the last visit will be recorded, including name of medication, route of administration, dosage, indication, and start and end dates where available. If any medications listed in [Appendix III](#) were used after the last visit without the proper washout period, the subject will be terminated;
- (3) Perform alcohol and drug test; if any is positive, subject will be terminated;
- (4) Subjects will be trained again on the use of the MDI inhalation aerosols prior to each treatment session, as described in [Section 4.5.1](#);
- (5) Placement of ECG leads;
- (6) Subjects need to rest for at least 10 minutes prior to the baseline vital signs evaluations. Vital signs should be taken from the opposite arm of the IV catheter arm if possible; Vital signs measurement may be repeated twice to PI discretion.
- (7) An indwelling IV catheter shall be placed into one of the antecubital region veins for blood drawing, or separate venipunctures may be used; and
- (8) One (1) baseline blood samples will be collected within 30 minutes before dosing.

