5.3.7. Safety Evaluations/Monitoring

The following safety measurements will be performed during each Dosing Visit:

- (1) Vital signs (HR, SBP/DBP): at baseline, 5±2 min, 15±5 min, 60±5 min, 120±15 min and 24 ±2 hrs post-dose.
- (2) 12-lead ECG (routine QT and QTc analysis): at baseline, 20±5 min, 120±15 min and 24 ±2 hours post-dose.
- (3) Serum potassium and glucose levels will be measured at baseline, 10±2 min, 60±5 min, and 24 ± 2 hrs post-dose.
- (4) All subjects will be queried for adverse events (AEs) and AEs must be recorded with all related information.

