5.3.3 Safety Assessment

Safety will be assessed by tabulation of Adverse Events and will be presented with descriptive statistics at Baseline and each treatment arm. Adverse events will be summarized by treatment group. Treatment groups will be compared with respect to the incidence of each type of adverse event observed.

The n, mean and standard deviation of serum potassium and glucose, SBP/DBP, HR and ECG readings will be summarized per treatment arm by time of testing. The frequency count and percentage of whether any significant changes in physical exam, ECG and Lab results since screening visit will be reported at the end of study.

Any early termination will be listed with primary reasons per treatment arm as part of the safety assessment.

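### The stated comparison for vital-sign and ECG changes refers to Screening, and no individual change from each dosing visit's own pre-dose reading is defined

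*Protocol*

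**What the plan says.** **The stated comparison.** Protocol 6.3, item (1), reads: "Changes in vital signs and ECG will be analyzed between Screening, designated post-dose time points and EOS". Part VI, item 1, of the synopsis has the same rule: "Monitor changes in vital signs and ECG will be analyzed between Screening, designated post-dose time points and EOS". Neither mentions a pre-dose reading from the dosing visit.

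**What is measured.** Protocol 5.3.7 opens with "The following safety measurements will be performed during each Dosing Visit" and then lists "Vital signs (HR, SBP/DBP): at baseline" and "12-lead ECG (routine QT and QTc analysis): at baseline", each followed by post-dose times. Protocol 5.3.2 standardises the pre-dose vital signs: "Subjects need to rest for at least 10 minutes prior to the baseline vital signs evaluations". SAP 3.2.2 also lists the pre-dose reading for both.

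**The neighbouring item.** For the two serum measurements, Protocol 6.3, item (2), does name a baseline: "Changes in serum potassium and glucose at study baseline, designated post-dose time points and EOS". It does not say whether this is the baseline of each visit.

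**The SAP.** Section 5.3.3 gives n, mean and SD of blood pressure, heart rate and ECG readings per treatment at each time of testing. It defines no change from the pre-dose value. It separately counts significant changes in physical examination, ECG and laboratory results "since screening visit will be reported at the end of study". Vital signs are not in that count.

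**The concern.** The expected cardiovascular effects of epinephrine are increases in heart rate and blood pressure (Protocol 1.5.3), and the schedule looks for them within minutes of dosing. The natural reference for such an effect is a reading taken shortly before the dose, under the same conditions. The trial collects that reading at every visit, but the protocol's analysis text names Screening instead.

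Screening is earlier, and the conditions differ. Dosing visits involve check-in the night before, a fast of at least 10 hours, 24 hours without caffeine (Protocol 5.2.4), a blood-sampling catheter or venipuncture (5.3.2), and dosing between 07:00 and 11:00 (5.3.4). No caffeine restriction or clock window is stated for Screening. Screening blood pressure, heart rate and QTcF also serve as eligibility criteria, which invites some regression to the mean.

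What is at stake is the description of acute change within each treatment. A change from Screening combines the drug effect with any shift between the Screening day and the dosing day, and it carries day-to-day noise. Without individual changes from pre-dose, the report would also lack their SD and any count of subjects with large changes in heart rate, blood pressure or QTc.

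**Working it through.** The documents give no SD, correlation or target figure on this point, so there is no planned number to reproduce. The counts and intervals below come from the documents. The variance inputs are assumptions.

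**1. Is a same-visit reference available?** Vital signs: 1 pre-dose + 5 post-dose (5, 15, 60 and 120 min, 24 h) = 6 per visit. ECG: 1 pre-dose + 3 post-dose (20 and 120 min, 24 h) = 4 per visit. Both match Protocol Table 4, so the reference is planned in every period.

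**2. How far away is Screening?** Screening is 3–7 days before Visit 1 (Protocol 5.2.1), and visits are 2–7 days apart (5.2.4).
- Visit 1: 3 to 7 days
- Visit 2: 3 + 2 = 5 to 7 + 7 = 14 days
- Visit 3: 3 + 2 + 2 = 7 to 7 + 7 + 7 = 21 days

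**3. Effect of a shift.** Let a reading be subject + day + within-day error. Post-dose minus Screening then estimates drug effect + shift. Post-dose minus pre-dose estimates the drug effect, because the day term cancels. With an assumed effect of +5 and an assumed shift of −3, change from Screening averages 5 − 3 = +2 and change from pre-dose averages +5.

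**4. SD of within-treatment change.** With equal variances σ² and correlation ρ between the two readings, the SD of their difference is σ√(2(1 − ρ)). The ratio of the same-visit SD to the Screening SD is √((1 − ρw)/(1 − ρb)), where ρw is the correlation within a visit and ρb the correlation between days.

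**5. SD of the within-subject A-minus-B contrast.** Screening is the same value in both changes and drops out, which leaves post-dose A minus post-dose B with variance 2σ²(1 − ρb). With pre-dose change scores the variance is 4σ²(1 − ρw). The SD ratio is √(2(1 − ρw)/(1 − ρb)). With the pre-dose value as a covariate it is √(1 − d²), where d = (ρw − ρb)/(1 − ρb) is the between-day share of within-subject variance. That last formula ignores the small cost of estimating the slope.

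Results over assumed ρw of 0.7–0.8 and ρb of 0.5–0.6:

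| ρw / ρb | d | Within-treatment SD ratio | Reduction | A−B ratio, change score | A−B ratio, covariate |
|---|---|---|---|---|---|
| 0.8 / 0.5 | 0.60 | √(0.2/0.5) = 0.63 | 37% | √(0.4/0.5) = 0.89 | 0.80 |
| 0.8 / 0.6 | 0.50 | √(0.2/0.4) = 0.71 | 29% | √(0.4/0.4) = 1.00 | 0.87 |
| 0.7 / 0.5 | 0.40 | √(0.3/0.5) = 0.77 | 23% | √(0.6/0.5) = 1.10 | 0.92 |
| 0.7 / 0.6 | 0.25 | √(0.3/0.4) = 0.87 | 13% | √(0.6/0.4) = 1.22 | 0.97 |

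**6. In measurement units.** Assume a within-subject SD of 8 for one reading and n = 24. Change from Screening has SD 8√2 = 11.3, and the 95% half-width of the mean is 1.96 × 11.3/√24 = 4.5.

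| Between-day share d | SD, same-visit change: 11.3√(1 − d) | Half-width |
|---|---|---|
| 0% | 11.3 | 4.5 |
| 25% | 9.8 | 3.9 |
| 50% | 8.0 | 3.2 |
| 75% | 5.7 | 2.3 |

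If there is no between-day variance, the same-visit reference gains nothing in precision.

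**The case against.** **The SAP already shows the pre-dose values.** This stands. SAP 5.3.3 summarises readings by time of testing, the pre-dose reading is one of those times in SAP 3.2.2, and synopsis VI, item 2, lists it for heart rate and blood pressure. With complete data, mean change is the difference of two tabulated means. A reader might infer that the pre-dose readings go unused, but the documents do not support that. What is missing is individual change, its SD and counts of large changes.

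**The protocol wording is loose.** Item (1) of 6.3 lists occasions to compare and does not spell out post-dose minus Screening. The SAP's Screening-referenced count covers ECG but not vital signs, and it is an end-of-study check. The SAP's output template is available only on request and may contain change tables. All of this tempers the criticism. Even so, the pre-dose reading is absent from the item that governs these changes, and the SAP text does not supply the definition.

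**The treatment comparison is unaffected.** A reader might infer that a Screening reference biases the comparison of inhaled with injected epinephrine. It does not, since the Screening value cancels within subject. Nor does a simple change score reliably sharpen that comparison: on the assumptions above, its SD runs from 11% smaller to 22% larger.

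**Screening has a proper use.** This also stands. Vital signs and ECG are scheduled at Screening and at EOS, and comparing the two is a reasonable overall check. Nothing here argues for dropping it.

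**Conclusion.** The point holds as a gap in definition. As written, the protocol refers acute vital-sign and ECG changes to a reading taken 3 to 21 days before the dose under different conditions, and neither document defines the individual change from the pre-dose reading collected at each visit. Any Screening-to-dosing-day shift passes in full into each treatment's reported change.

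The SD of within-treatment change would be 13% to 37% smaller with the same-visit reference. That range rests on assumed correlations, equal variances and a single between-day correlation. It is least certain for the 24-hour reading, which falls on the next day.

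The analysis is descriptive and concerns safety only. No test, margin or PK endpoint depends on it. The change is still worth making, because it needs no new data and bears on the acute responses that the safety schedule is built to capture.

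**What to change.** In Protocol 6.3, item (1), synopsis VI, item 1, and SAP 5.3.3:

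- Define acute change in heart rate, systolic and diastolic pressure and ECG intervals as the post-dose value minus the same-visit pre-dose value. Summarise it by treatment and time point with n, mean and SD, and add a count of large changes against thresholds set in advance.
- In any between-treatment comparison of these measures, use the same-visit pre-dose value as a covariate and do not rely on the simple change score.
- Keep the Screening-to-EOS comparison, including for vital signs and ECG, and label it as an overall safety check.

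The cost is a few sentences and one derived variable per measure. No visit, procedure or sample is added.

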6.4. Interim Analyses

No interim analyses are planned for this study.

7. STUDY MANAGEMENT

7.1. Discontinued Subjects or Withdrawal

Subjects can withdraw or be withdrawn from the study at any time. In addition, it may be necessary to discontinue subjects from the study due to medical safety considerations, noncompliance or administrative concerns.

If for any reason a subject is withdrawn or discontinued before completing the study, the reasons for withdrawal or discontinuation must be entered on the End-of-Study and/or Subject Withdrawal or Discontinuation source document page.

7.2. Adverse Events

The Investigator will be required to provide the sponsor with any information concerning any findings that suggest any adverse event pertinent to the investigation.

The study may be stopped at any time due to safety concerns. Subject safety will be constantly monitored throughout the study. However, if and when a significant safety concern arises, such as occurrence of serious and unexpected adverse drug events that are considered associated with the study drug(s) per regulatory guidelines and SOP, the study may be discontinued and safety will be reviewed.

Any such safety analysis will be presented and discussed in the final study report.

7.2.1. Types of Adverse Events

The term “adverse event” could include any of the following events that arise, or increase in severity and/or frequency, during the course of the study:

- a) Any signs or symptoms whether thought to be related or unrelated to the condition under study.
- b) Any clinically significant laboratory abnormality.
- c) Any physical abnormality detected.

These data will be recorded on the appropriate case report forms, including “Adverse Event Form”, regardless of whether they are thought to be associated with the study or the drug under investigation. Per FDA definition, “associated with the use of the drug” means that “there is a reasonable possibility that the experience may have been caused by the drug”.

An adverse event is considered associated with the use of the drug if the attribution is possible, probable, or very likely according to definitions specified in the AE reporting SOP and the CRF for adverse event.

Signs or symptoms will be graded by the Investigator as mild, moderate or severe according to the following definitions:

Severity	Definition
Mild	Causing no limitation of usual activities
Moderate	Causing some limitation of usual activities
Severe	Causing inability to carry out usual activities

When a subject experiences any significant adverse event or laboratory abnormality, the event must be followed based on good clinical practice until it becomes resolved or stable.

7.2.2. Definition of Serious and Unexpected Adverse Events

According to the FDA guidelines, a serious adverse event will refer to any adverse drug experience occurring at any dose results in any of the following outcomes:

- a) Cancer^[6].
- b) Death.
- c) A life-threatening adverse drug experience.
- d) Hospitalization or prolongation of existing hospitalization.
- e) A persistent or significant disability/incapacity.
- f) A congenital anomaly/birth defect.
- g) Other important medical events, while not resulting in death, being life-threatening, or requiring hospitalization, may still be considered as serious adverse events when, based upon appropriate medical judgment, they may jeopardize the patient or subject and may require medical or surgical intervention to prevent one of the outcomes listed in this definition.

An unexpected event is any adverse experience, the specificity or severity of which is not consistent with the approved labeling. “Unexpected”, thus refers to an adverse drug experience that has not been previously observed rather than from the perspective of such experience not being anticipated from the pharmacological properties of the pharmaceutical product.

Expected adverse events of Primatene Mist include: headache, nausea, vomiting, nervousness, dizziness, shaking (tremor), trouble sleeping, stomach upset, sweating, dry mouth, bad taste, cough, sore throat, difficult or painful urination, fast heartbeat, weakness, high blood pressure, loss of appetite, loss of skin color, or dry throat. Severe adverse reactions are very rare.

7.2.3. Obligations of AE Reporting to Sites, FDA and IRB

Sponsor Reporting to Investigator: Sponsor shall promptly notify the Investigators of any material discoveries made during monitoring of the sites which could affect the safety of participants or influence the conduct of the study.

Investigator Reporting to Sponsor: Any serious events, whether or not unexpected or considered to be associated with the use of the drug, must be communicated by the Investigator to Amphastar Pharmaceuticals, Inc. immediately upon discovery of the event. The Clinical Research Associate (CRA) will then advise the Investigator regarding the nature of any further information or documentation that is required.

Sponsor/Investigator Reporting to FDA: It is required to report to FDA any serious adverse event observed during the conduct of the study, regardless of whether the event is considered drug related.

Each notification shall be made as soon as possible and in no event later than 15 calendar days after the sponsor's initial receipt of the information. Each notification shall be submitted via the FDA Safety Reporting Portal (SRP). The FDA must be notified via telephone of the Sponsor's initial notification of any fatal or life-threatening experiences associated with the use of the drug as soon as possible but in no event later than seven (7) calendar days.

Sponsor/Investigator Reporting to IRB: All serious adverse events or an unanticipated problem must be reported to the appropriate IRB/Ethics Committee promptly.

1. Serious Adverse Event (SAE) Reporting Policy:

An adverse event is considered **serious** if it results in any of the outcomes listed in [Section 7.2.2](#). Study sites are required to report any SAE to the IRB, regardless of whether the event is considered drug related. The specific reporting policy defined by the IRB will be followed for the reporting of SAE to IRB within the required time period.

Note: IRB does not require the event to be unexpected. The IRB feels that this category is too subjective, and can change over time, to be a criterion for deciding whether the event is reportable or not.

2. Unanticipated Problem/Event Report Form:

In order for the event to be reportable to the IRB, it must meet all of the following criteria:

- The event is unexpected (in terms of nature, severity, or frequency) given the research procedures described in the study Protocol and/or Informed Consent

Form.

- The event is related or possibly related to participation in the research study.
- The event suggests that the research places subjects or others at a greater risk of harm than was previously realized or anticipated.

It is required to report unanticipated problem(s) to the IRB promptly after the Investigator becomes aware of them. The specific reporting policy defined by the IRB will be followed for the reporting of unanticipated problem to IRB within the required time period.

Sponsors are specifically required to “keep each participating Investigator informed of new observations discovered by or reported to the sponsor on the drug, particularly with respect to adverse effects and safe use”.

7.2.4. Follow-up of Adverse Events

The Sponsor’s CRA will periodically request follow-up information of the AE from the PI. The CRA will ensure that all fatal or serious adverse events are reported to the IRB, per Amphastar SOP. All serious adverse events must be followed up for at least 30 days or until resolved or having become stable.

The sponsor shall promptly investigate all safety information received by it from the clinical studies. Follow up information to a safety report shall be submitted as soon as the relevant information becomes available.

